# NL62337.029.17 / ParoSysACTA

Periodontitis as signal for an underlying disease

# LIST OF ABBREVIATIONS AND RELEVANT DEFINITIONS

ABR	ABR form, General Assessment and Registration form, is the application
	form that is required for submission to the accredited Ethics Committee
	(In Dutch, ABR = Algemene Beoordeling en Registratie)
ΑСТА	Academic Centre for Dentistry Amsterdam
ADA	American Diabetes Association
ASCVD	Atherosclerotic Cardiovascular Disease
BMI	Body Mass Index
CDC-AAP	Centers for Disease Control and Prevention
DM	Diabetes Mellitus
ESC	European Society of Cardiology
HbA1c	Glycated Haemoglobin
HDL-C	High-density Lipoprotein Cholesterol
IC	Informed Consent
IDF	International Diabetes Federation
LDL-C	Low-density Lipoprotein Cholesterol
MetS	Metabolic Syndrome
METC	Medical research ethics committee (MREC); in Dutch: medisch ethische
	toetsing commissie (METC)
NHG	Nederlands Huisartsen Genootschap (Dutch Family Physicians Clinical
	Practical Guidelines)
NCEP	National Cholesterol Education Program (NCEP) expert panel on
ATP III	detection, evaluation, and treatment of high blood cholesterol in adults
	(Adult Treatment Panel III)
OSA	Obstructive Sleep Apnea
OSAS	Obstructive Sleep Apnea Syndrome
Sponsor	The sponsor is the party that commissions the organisation or
	performance of the research, for example a pharmaceutical
	company, academic hospital, scientific organisation or investigator. A
	party that provides funding for a study but does not commission it is not
	regarded as the sponsor, but referred to as a subsidising party.
STROBE	Strengthening the Reporting of Observational studies in Epidemiology
WC	Waist Circumference
WMO	Medical Research Involving Human Subjects Act (in Dutch: Wet Medisch-
	wetenschappelijk Onderzoek met Mensen

### SUMMARY

**Rationale:** Diabetes Mellitus (DM), Atherosclerotic Cardiovascular Disease (ASCVD), Metabolic Syndrome (MetS) and Obstructive Sleep Apnea Syndrome (OSAS) are major health problems (1-3). However due to absence of symptoms and/or lack of knowledge, people are often unaware of having DM, ASCVD, MetS or OSAS while early treatment could prevent the progression of these diseases. Therefore, risk indicators for early detection of DM, ASCVD, MetS and OSAS are needed and proposed (4-8).

Many studies demonstrate the association between oral diseases and DM and/or ASCVD (9, 10). The most observed chronic oral disease is periodontitis. Periodontitis is a common chronic multifactorial inflammatory disease of the supporting structures of the teeth (11). DM and ASCVD might, due to their pro-inflammatory state and alteration of the immune system, contribute to the onset and/or progression of periodontitis (12). Therefore periodontitis could be considered as an early sign of an underlying vascular and/or metabolic pathology (13).

Some studies have also reported a positive association between periodontitis and MetS (14). The MetS prevalence in patients with periodontitis was shown to be higher than controls and MetS showed to be associated with severe periodontitis (15, 16). The association between periodontitis and OSAS is less established, however there is some evidence to a plausible association between periodontal disease and Obstructive Sleep Apnea (OSA) (8).

Due to the broad overlap of objective biomarkers, in this study, subjects with or without periodontitis will be screened for determining the prevalence of (pre)DM, the 10-year-risk of ASCVD, the prevalence of MetS and the risk of OSAS. The screening will be based on clinical measures, specific blood markers determined by a developed finger stick analysis and three questionnaires.

Notably, a recently published pilot paper from our research group presents the feasibility and preliminary results of proposed screening for (pre)DM; we found 18.1% new DM cases among subjects with severe periodontitis compared to 9.9% in mild/moderate periodontitis and 8.5% in controls (13).

**Objective**: The aim of the proposed study is to screen for (pre)DM, an increased 10-year-risk of ASCVD, MetS and a high risk of OSAS in subjects with and without periodontitis.

Study design: Cross-sectional study

**Study population:** In total 783 patients will be included (261 without periodontitis, 261 with mild/moderate periodontitis and 261 with severe periodontitis) at the Academic Centre for Dentistry Amsterdam (ACTA). The subjects with periodontitis that will be enrolled in this study are referred to the periodontal clinic for diagnosis and treatment of periodontitis. The subjects without periodontitis will be selected among individuals that visit the dental school for regular dental checkups. All subjects will be 18 years and older and are mainly inhabitants from Amsterdam and surrounding areas.

**Intervention (if applicable)**: Subjects with and without periodontitis will undergo the following intervention:

- General, medical and dental histories (standard procedure)
- Clinical periodontal evaluation (standard procedure)
- Dental x-rays, when indicated for periodontitis or other dental pathology (standard procedure)
- Measurement of systolic and diastolic blood pressure (standard procedure)
- Measurement of length and body weight, waist and neck circumference, a questionnaire for demographic characteristics, an International Physical Activity Questionnaire (IPAQ) and an OSAS risk questionnaire (extra procedure)
- Plasma finger stick procedure (HemCol, Labonovum BV) for measuring biomarkers: A drop of blood is obtained with a finger stick (Greiner Bio-one Safety Lancet) and collected in a collection tube. The collection tube is sent to the laboratory for analysis by regular mail. (extra procedure)

**Main study parameters/endpoints:** To investigate, within a dental setting, the differences between subjects with and without periodontitis in:

- The prevalence of preDM and DM
- The 10-year-risk of ASCVD
- The prevalence of MetS
- The risk of OSAS

# Nature and extent of the burden and risks associated with participation, benefit and group relatedness:

- The extra burden for the subjects with and without periodontitis will be three questionnaires, measurement of length, body weight, waist and neck circumference, and a finger stick procedure.
- The risks associated with participation are negligible.
- Possible benefit of participation will be early detection of health risks such as (pre)DM, ASCVD, MetS, OSAS and possibly a referral for further diagnosis and/or treatment at the family physician.

## 1. INTRODUCTION AND RATIONALE

Diabetes Mellitus (DM), Atherosclerotic Cardiovascular Disease (ASCVD), Metabolic Syndrome (MetS) and Obstructive Sleep Apnea Syndrome (OSAS) are major health problems (1-3). However due to the absence of symptoms and/or disease-related knowledge, the pathology of DM, ASCVD, MetS and OSAS often goes undetected. Approximately one-third of the people with DM are not aware of their status (17). Another study has shown that the onset of DM appears approximately 4 to 7 years before clinical diagnosis (18). Research in Dutch OSAS patients showed that in 66% of the patients it took ≥4 years before they were diagnosed with OSAS (4). Therefore, risk indicators for DM, ASCVD, MetS and OSAS are needed and proposed (4-8). In this respect the onset of several oral pathologies might be indicative.

Many studies demonstrate the association between oral diseases and DM and/or ASCVD (9, 10). The most observed chronic oral disease is periodontitis. For MetS and OSAS this association is less clear (8). However different studies have suggested an association between periodontitis and MetS (14-16) or between periodontitis and OSAS (8, 19). Periodontitis is a common chronic multifactorial inflammatory disease of the supporting structures of the teeth (root cementum, gingiva, periodontal ligament and alveolar bone). This condition is initiated and sustained by an aberrant host immune response against resident bacterial biofilms on the teeth and the tooth roots (11). Although the relative contribution of several causal factors may vary among patients, the uncontrolled inflammatory response upon bacterial accumulation seems the major factor determining the onset and/or progression of the periodontitis (12). In this respect, an increased proinflammatory state caused by processes like atherosclerosis and metabolic dysregulation might contribute to the onset and/or progression of periodontitis. Therefore periodontitis could be considered as an early sign of an underlying vascular and/or metabolic pathology (13). With this knowledge, it has been suggested that dentists could help to screen for DM, the risk of ASCVD, MetS and the risk of OSAS.

Notably, today there are several easy accessible and non-invasive techniques to screen for DM, ASCVD, MetS and OSAS. For DM there is the convenient Haemoglobin A1c (HbA1c) level, which is put forward by the American Diabetes Association (ADA) and International Diabetes Federation (IDF) as indicative of the metabolic state: prediabetes (HbA1c: 39-47 mmol/mol) and diabetes (HbA1c: ≥48 mmol/mol) (5,6). For ASCVD there is the "10-year-risk" chart, based on age, gender, total cholesterol, HDL cholesterol (HDL-C), LDL cholesterol (LDL-C), systolic and diastolic blood pressure, smoking, presence of diabetes and rheumatoid arthritis (according to the NHG standards, which are the European Society of Cardiology guidelines modified to the Dutch population)(20). The diagnostic criteria for MetS are based on waist circumference (WC), triglycerides (TG), HDL-C, hypertension and dysglycemia (according to the NCEP ATP III) (21). For OSAS there is the recently developed OSAS risk questionnaire, which scores patients into a low, moderate or high risk category of having OSAS (22).

### NL62337.029.17 / ParoSysACTA Periodontitis as signal for an underlying disease

The majority of dental practices is not equipped for blood chemistry, however, today all plasma markers can be measured easily and accurately with help of a finger stick procedure (HemCol, Labonovum B.V., Rotterdam, The Netherlands). The measurement of the HbA1c and lipid by finger stick procedure is an elegant and essentially non-invasive way to screen for DM, ASCVD and MetS biomarkers. In addition, other demographic parameters (such as age, gender, smoking and rheumatoid arthritis) are known from the medical history and obtained with a questionnaire. Also systolic and diastolic blood pressure, Body Mass Index (BMI), Waist Circumference and N (WC) will be measured. A dental office, and in particular the dental office with a high volume of periodontitis patients, could be a suitable location for screening of individuals for early signs of DM, ASCVD, MetS and OSAS.

The importance of early identification of subjects with increased risk for DM, ASCVD and MetS lies in the prevention of DM associated micro- and macrovascular complications, future coronary heart disease and/or cerebrovascular events. Early identification in OSAS patients would result in better medical and psychological conditions. Therefore, it contributes to an increased quality of life of our patients. The results of the current study should indicate the prevalence of DM and MetS and the prevalence of patients being at increased risk for ASCVD or OSAS. This may form the basis for further studies into general applicability and cost-effectiveness.

### Hypothesis

- We put the hypothesis forward that periodontitis patients show an increased prevalence of (pre)DM, an increased 10-year-risk of ASCVD, an increased prevalence of MetS and an increased risk of OSAS compared with subjects without periodontitis.

Notably, a recently published pilot paper from our group presented the feasibility and preliminary results of proposed screening for (pre)DM; we found 18.1% new DM cases among subjects with severe periodontitis compared to 9.9% in mild/moderate periodontitis and 8.5% in controls (13).

# 2. OBJECTIVES

Primary Objective:

To investigate, within a dental setting, the differences between subjects with and without periodontitis in:

- The prevalence of preDM and DM (established cut-off values for HbA1c, appendix 1 and 2 (7))
- The 10-year-risk of ASCVD ("10-year-risk" chart, appendix 3 (20))
- The prevalence of MetS (diagnostic criteria of NCEP ATP III, appendix 4 (21))
- The risk of OSAS (OSAS risk questionnaire (22))

Secondary Objective(s):

- To investigate the differences in (pre)DM prevalence, 10-year-risk of ASCVD, MetS prevalence and OSAS risk between mild/moderate and severe periodontitis patients

### 3. STUDY DESIGN

A cross-sectional study will be performed with a duration of 24 months at the dental clinic of the Academic Centre for Dentistry Amsterdam (ACTA).

### 4. STUDY POPULATION

# 4.1 Population (base)

The research population will be drawn from the patients that visit the ACTA. These patients are particularly from Amsterdam and surrounding areas. The study subjects with periodontitis that will be enrolled in this study are referred to the periodontal clinic of ACTA for diagnosis and treatment of periodontitis. The control subjects without periodontitis will be selected among subjects that visit the dental school of ACTA for regular dental checkups.

# 4.2 Inclusion criteria

In order to be eligible to participate in this study, a subject must meet all of the following criteria:

- Age ≥ 18 years
- (Patient) referred for periodontitis
- (Control) visiting the dental school for regular dental check-up without periodontitis
- Able and willing to give written informed consent and comply with the requirements of the study protocol.

# 4.3 Exclusion criteria

A potential subject who meets any of the following criteria will be excluded from participation in this study:

- None

### 4.4 Sample size calculation

The calculation of the sample size was based on a  $Chi^2$ -test having an  $\alpha$ <0.05 with 90% power and using the prevalence of diabetes of two groups (without periodontitis: 8.5%, severe periodontitis: 18.1%)(13). The required sample size is a minimum of 261 subjects per group.

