7.8 Drug accountability

### 8. METHODS

### 8.1 Study parameters/endpoints

### 8.1.1 Main study parameter/endpoint

To investigate, within a dental setting, the differences between subjects with and without periodontitis:

- The prevalence of preDM and DM (established cut-off values for HbA1c, appendix 1 and 2 (7))

- The 10-year-risk of ASCVD ("10-year-risk" chart, appendix 3 (20))
- The prevalence of MetS (diagnostic criteria of NCEP ATP III, appendix 4 (21))
- The risk of OSAS (OSAS risk questionnaire (22))

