### NL62337.029.17 / ParoSysACTA Periodontitis as signal for an underlying disease

### **10. STATISTICAL ANALYSIS**

The prevalence of (pre)DM and MetS, the 10-year risk of ASCVD and the risk of OSAS will be presented in tables. First, one table will be generated describing the background variables, blood chemistry and demographic characteristics. Secondly, the prevalence of (pre)DM and MetS, the 10-year-risk of CVD and the OSAS risk will be reported in patients with and without periodontitis.

According to the ADA guidelines HbA1c values will be classified as normal (<5.7% [<39 mmol/mol]), preDM (5.7-6.4% [39-47 mmol/mol]) and DM (≥6.5% [≥48 mmol/mol]) (7).

The 10-year risk of ASCVD will be assessed with help of the risk table from the Dutch guideline on cardiovascular risk management (CVRM) according to the standards of the Dutch College of General Practitioners (NHG) (20). The NHG standards are derived from European Society of Cardiology guidelines and modified to the Dutch situation (6).

According to the NCEP ATP III guidelines MetS is present if three of the 3 or more of the five criteria are met: elevated waist circumference over  $\geq$  102 cm (men) or  $\geq$  88 cm (women), triglyceride (TG) level over  $\geq$  1.7 mmol/L or being on drug treatment for elevated TG, high density lipoprotein cholesterol (HDL-C) level less than < 1.03 mmol/L (men) or < 1.3 mmol/L (women), blood pressure over 130/85 mmHg or on antihypertensive drug treatment, and blood glucose level over  $\geq$  5/6 mmol/L (21).

The OSAS risk is calculated with help of a new questionnaire (PhilipsQ) which is constructed from body measurements (sex, age, BMI, neck circumference) and the most predictive questions of the following OSAS and sleep questionnaires: Berlin Questionnaire (BerlinQ), STOP Questionnaire (STOPQ) and Athens Insomnia Scale (AIS). An algorithm is developed to compute the individual estimated probability (p) that a subject will have OSAS: p(OSAS) = 1 / (1+e-X), where  $X = -6.322 + 2.828 \times AIS + 2.745 \times STOPBANGQ$  High + 0.965 × STOPBANGQ Intermediate + 4.640 × BerlinQ High + 1.584 × BerlinQ Intermediate + 0.790 × Age + 0.810 × BerlinQ Q-5. The final cutoff values were determined by exploratory logistic regression analyzes. The risk of OSAS will be classified as low (p[OSAS] < 35%), intermediate (p[OSAS] = 35-55%) and high (p[OSAS] > 55%) (22).

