### **10.1 Primary study parameter(s)**

The cases and controls are a priori defined by inclusion and exclusion criteria. The STROBE guideline will be followed and a flow diagram will be generated of how many individuals have been screened, invited to participate, included and analysed (29). All initially included study subjects will form part of the data analysis (intention to treat). Type I error will be controlled by including a sufficient number of cases and controls to avoid multiplicities and to apply Bonferroni corrections where applicable. Secondly, we have determined the minimal sample size on the basis of an appropriate power calculation (see chapter 4.4).

The prevalence of (pre)diabetes, the 10-year risk of ASCVD, the prevalence of MetS and the prevalences of OSAS risks (categorical variables) within the study population will be compared with parametric and non-parametric tests (ANOVA and  $Chi^2$ -test). Where applicable, analyses will be corrected for multiple testing (Bonferroni). The significance level will be set to p<0.05.

The prevalence of (pre)DM among cases and controls will be firstly reported without adjustment of any of potential covariates. In a second exploratory analysis we will adjust the prevalence for general and diabetes and ASCVD related characteristics of the study population: sex, age, ethnicity (origin of parents), education level, smoking habits, relatives with DM, history of periodontal treatment, diagnosis of hypertension, diagnosis of hypercholesterolemia, diagnosis of DM and the BMI, amount of physical activity.

The 10-year risk of ASCVD will be calculated according to the algorithm from the ESC guidelines, which is adapted to the Dutch situation. No further adjustments will be done.

The prevalence MetS will be calculated according to the criteria of the NCEP ATP III guidelines. No covariates will be included.

The risk for OSAS will be assessed by the OSAS questionnaire. No further adjustments will be done. However, the results will be explored in relation to having periodontitis, the

background characteristics, the blood chemistry outcomes and having (pre)diabetes and the 10-year risk for ASCVD.

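### The 90% power in Section 4.4 is for DM in severe versus no periodontitis, which is neither declared comparison; on the pilot new-DM rates, with versus without periodontitis has about 61%

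*Combined protocol and SAP*

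**What the plan says.** Section 4.4 bases the sample size on a chi-square test at alpha 0.05 with 90% power, "using the prevalence of diabetes of two groups (without periodontitis: 8.5%, severe periodontitis: 18.1"%), and arrives at 261 subjects per group. The Summary sets the recruitment target: "261 without periodontitis, 261 with mild/moderate periodontitis and 261 with severe periodontitis", 783 in all.

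The comparisons are declared elsewhere:

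- **Primary.** Section 2 reads "To investigate, within a dental setting, the differences between subjects with and without periodontitis in" and then lists four outcomes. The Summary and Section 8.1.1 repeat this, with the first outcome given as "The prevalence of preDM and DM (established cut-off values for HbA1c, appendix 1 and 2 (7"). The Hypothesis has the same two sides: periodontitis patients are expected to show, among other things, "an increased prevalence of MetS and an increased risk of OSAS compared with subjects without periodontitis". Section 10 follows suit: "the OSAS risk will be reported in patients with and without periodontitis".
- **Secondary.** Sections 2, 8.1.2 and 10.2 compare severe with mild/moderate periodontitis.

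The pilot rates for all three groups are in the Summary and the Hypothesis: "18.1% new DM cases among subjects with severe periodontitis compared to 9.9% in mild/moderate periodontitis and 8.5% in controls". Section 4.4 uses the first and the last of them.

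On multiplicity, Section 10.1 states: "Type I error will be controlled by including a sufficient number of cases and controls to avoid multiplicities and to apply Bonferroni corrections where applicable". It then cites Section 4.4 as the appropriate power calculation.

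**The concern.** Section 4.4 names its two groups openly, but does not say that they are not the groups of the primary objective. The mild/moderate group makes up half of the periodontitis side, and its pilot rate (9.9%) is close to the control rate (8.5%). Pooling it with the severe group cuts the expected DM difference from 9.6 to 5.5 percentage points. The extra 261 subjects on that side do not make up for this.

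A reader of Section 10.1 would take 90% as the power of the primary analysis. If the pilot rates hold, the declared comparison would miss the DM difference about four times in ten at 0.05, and a null result could be misread as no difference. Section 4.4 also uses an unadjusted 0.05, although Section 10.1 foresees Bonferroni correction without a divisor. Subject numbers do not control type I error in any case.

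**Working it through.** **Inputs.** Alpha 0.05 and 90% power (4.4; sidedness is not stated, and two-sided reproduces the plan's figure). New-DM rates 8.5%, 9.9% and 18.1% for none, mild/moderate and severe (Hypothesis). Groups of 261/261/261 (Summary).

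**Formulas (chi-square for two proportions, pooled variance under the null).** With difference d, group sizes n1 and n2, and size-weighted mean rate p̄:

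- s0 = √[p̄(1−p̄)(1/n1 + 1/n2)]
- s1 = √[p1(1−p1)/n1 + p2(1−p2)/n2]
- power = Φ[(d − z·s0)/s1], where z = 1.960 at two-sided 0.05
- equal-group size n = {[1.960·√(2p̄(1−p̄)) + 1.282·√(p1(1−p1) + p2(1−p2))]/d}²

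**1. The plan's own figure.** For 8.5% versus 18.1%, d = 0.096 and p̄ = 0.133. Then n = [(1.960 × 0.4802 + 1.282 × 0.4754)/0.096]² = 260.9, so 261 per group. Power at 261 per group is 90.0%. Section 4.4 is reproduced.

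**2. Declared primary comparison, DM.**

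- Rate with periodontitis: (9.9 + 18.1)/2 = 14.0%. Sizes: 261 + 261 = 522 versus 261.
- d = 0.140 − 0.085 = 0.055; p̄ = (261 × 0.085 + 522 × 0.140)/783 = 0.1217.
- s0 = 0.02478; s1 = 0.02299.
- Power = Φ[(0.055 − 1.960 × 0.02478)/0.02299] = Φ(0.28) = **61.0%**.

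| Two-sided alpha | Pooled formula | Simulated chi-square | Simulated, continuity-corrected | Unpooled formula |
|---|---|---|---|---|
| 0.05 | 61.0% | 61.8% | 56.9% | 66.7% |
| 0.025 (2 tests) | 49.1% | 49.8% | 44.7% | 56.0% |
| 0.0167 (3 tests) | 42.5% | 43.0% | 38.3% | 49.9% |
| 0.0125 (4 tests) | 38.2% | 38.8% | 33.6% | 45.8% |

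Simulations used 400,000 runs.

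**3. What 90% would take.** At 14.0% versus 8.5% and a 2:1 ratio, the group without periodontitis needs 525.4 subjects, so 526 + 1,052 = 1,578 against 783 planned. With 522 versus 261, the rate with periodontitis would have to be 16.7% against 8.5%.

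**4. Declared secondary comparison, DM.** For 18.1% versus 9.9% with 261 per group, d = 0.082, s0 = 0.03037 and s1 = 0.03016. Power = Φ(0.745) = **77.2%** at 0.05 and 58.1% at 0.0125. For 90%, n = 374.2, so 375 per group.

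**5. Sensitivity to the severity mix.** Holding 522 versus 261 and varying the share of severe cases:

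| Severe share | Rate with periodontitis | Power at 0.05 |
|---|---|---|
| 40% | 13.2% | 48.6% |
| 50% (planned) | 14.0% | 61.0% |
| 60% | 14.8% | 72.2% |
| 70% | 15.6% | 81.5% |

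**6. Contrasts that the plan does not declare.**

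| Test | Power at 0.05 | Power at 0.0125 |
|---|---|---|
| Severe versus none (formula) | 90.0% | 77.0% |
| Three-group chi-square (simulated) | 89.7% | 77.8% |
| Trend test, scores 0/1/2 (simulated) | 91.6% | 80.3% |

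**The case against.** The strongest reply is that this is really a three-group study. Recruitment is in three equal groups, Section 4.4 speaks of subjects per group, and Section 10.1 names ANOVA alongside the chi-square test, which suggests more than two groups. A three-group chi-square on the pilot rates has about 90% power, so on that reading 261 per group is adequate at 0.05. The reading is possible, but no three-group comparison is declared. Section 10.1 speaks of cases and controls, and Section 10.2 relabels mild/moderate disease as control only for the secondary aim. A three-group test would not answer the with-versus-without question either.

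Second, 61% is not the power of the whole declared endpoint. That endpoint is preDM and DM with nobody excluded, whereas the pilot rates are for new DM. This stands as a limit: power for combined preDM/DM could be higher or lower. But DM is the only outcome the plan powers, so it is the only one on which the 90% can be tested.

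Third, the 14.0% depends on an even severity mix, while Section 8.3 invites all periodontitis patients. That also stands, but power stays below 90% across the severe shares tried, 40% to 70%.

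Finally, the multiplicity wording is a separate matter. The mismatch does not depend on it, although the divisor decides which power should be quoted.

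**Conclusion.** The concern holds. The stated 90% belongs to neither the primary nor the secondary comparison, yet Section 10.1 relies on it for the primary parameters. For new DM, power is about 61% for the primary comparison at two-sided 0.05 (57% to 67% by test variant), falling to 38% by the pooled formula if Bonferroni covers four tests. It is about 77% for the secondary comparison at 0.05. This assumes the pilot rates and the planned 261/261/261 recruitment. Power for combined preDM/DM, ASCVD risk, MetS and OSAS risk cannot be computed from the documents. The data would remain usable, so this should be fixed but does not invalidate the design.

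**What to change.** **Default, keeping the comparisons as written.** Add to Section 4.4:

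> The 90% power refers only to DM in severe versus no periodontitis at unadjusted two-sided alpha 0.05. For DM in the primary comparison (522 with versus 261 without), the pilot new-DM rates give 14.0% versus 8.5% and about 61% power at 0.05 (57% to 67% depending on the test variant; 49% to 81% if 40% to 70% of cases are severe). For DM in the secondary comparison they give about 77%. No rates were available for combined preDM/DM, ASCVD risk, MetS or OSAS risk.

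In Section 10.1, delete the statement that subject numbers control type I error, and state which tests the Bonferroni correction covers and its divisor. Quote the power at that level in Section 4.4.

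Cost: wording only, with no extra subjects. The quoted power becomes less favourable, and the design itself is not strengthened.

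**Alternative, also without extra subjects.** Declare as the primary DM comparison either severe versus none, the contrast already sized, or a trend test across the three ordered groups. Cost: the Summary, the Hypothesis and Sections 2, 8.1.1, 10 and 10.1 must be amended. DM has to be separated from the other three outcomes, which now share one stem. Neither option estimates the with-versus-without difference, and severe versus none leaves the 261 mild/moderate subjects out of the primary DM test.
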